**ABBREVIATIONS AND DEFINITIONS OF TERMS**

Abbreviation	Definition of Term
AAD	American Academy of Dermatology
AJCC	American Joint Committee on Cancer
BCC	Basal Cell Carcinoma
°C	Degrees Celsius
CAP	College of American Pathologists
CM	Centimeters
EBT	Electronic Brachytherapy
ECT	Electrochemotherapy
ED&C	Electrodesiccation and Curettage
HIPAA	Health Information Portability and Accountability Act
HIV	Human Immunodeficiency Virus
HPV	Human Papilloma Virus
MMS	Mohs Micrographic Surgery
NCCN	National Comprehensive Cancer Network
NMSC	Non-Melanoma Skin Cancer
PDT	Photodynamic Therapy
PHI	Protected Health Information
RT	Radiation Therapy
SCC	Squamous Cell Carcinoma
SRT	Superficial Radiation Therapy
U.S.	United States
U.S. FDA	United States Food and Drug Administration
UV	Ultraviolet

## **ABSTRACT**

### Context

Non-melanoma skin cancer (NMSC) is the most common cancer in the United States (U.S.), with prevalence and incidence rapidly rising. Superficial radiation therapy (SRT) has been used for the treatment of NMSC since the 1900s, though its use declined since the development of Mohs micrographic surgery. With advances in radiation technology, there is a resurgence in the use of radiation therapy, more specifically, superficial radiation therapy in the treatment of NMSC. Superficial radiation therapy provides a viable treatment for NMSC but current literature on efficacy and long-term cure rates are needed.

### Objectives

- The primary objective of this retrospective analysis is to evaluate long-term efficacy and safety of SRT when applied with the Sensus Healthcare SRT-100™ in the treatment of NMSC.
- The secondary objectives of this study are to evaluate the data for potential differences in cure rates with respect to lesion variables (tumor size, location and type) and patient demographics; and to evaluate the relationship between outcomes and treatment dosage/fractionation.

### Study Design

- The study is a retrospective data registry design.
- The data will be used only as applicable to the objectives of this study.

### Setting/Participants

- Retrospective data will be collected from medical records of patients treated for NMSC with the SRT-100™ prior to January 1, 2015, with follow-up data available.
- There will be multiple participating study sites in the United States who have access to the required patient population medical records.
- The number of participants will be determined by the number of qualifying patient files identified cross all participating sites.
- Medical record retrospective data will be included for males and females treated with SRT-100™ prior to January 1, 2015

- January 1, 2015 and for whom follow-up data is available. Subjects will have NMSC pathological diagnosis of confirmed squamous cell carcinoma (SCC) or basal cell carcinoma (BCC) with Histopathological Grade of G1 (well differentiated); G2 (moderately differentiated) or Gx (not assessed in report), Qualifying subjects had a single lesion treated, or more than one lesion treated with a minimum 5 mm gap between the edges of the lesion margins.

#### Data/Specimen Collection Procedures and Frequency

- Study data will be retrospectively collected from already existing documentation in patient files at the participating sites.
- Study staff will perform an initial review of the existing patient charts for patients who were treated with SRT-100™ for NMSC prior to January 1, 2015. The selected charts will be further reviewed for satisfaction of inclusion criteria and presence of required data elements. The study staff will extract the required information from the patient charts and enter it into an Excel database provided by the study Sponsor.
- The data elements of patient demographics, lesion diagnostic variables and characteristics, lesion size and margins, treatment duration, treatment dosage and schedule, treatment outcomes (particularly cured vs, non-cured) and follow-up outcome variables (particularly incidence of lesion recurrence) will be recorded.
- Data collection will be ongoing until no additional qualifying patient charts are identified at the respective study sites.

## **1 INTRODUCTION AND BACKGROUND INFORMATION**

### **1.1 STUDY CONDITION: NON-MELANOMA SKIN CANCERS (NMSC)**

Non-Melanoma Skin Cancers (NMSC) predominantly (98%) include Basal Cell Carcinomas (BCC) and Squamous Cell Carcinomas (SCC).

### **1.2 BASAL CELL CARCINOMA (BCC)**

Basal cell carcinomas (BCC) are abnormal, uncontrolled growths or lesions that arise in the skin's basal cells that line the deepest layer of the epidermis. BCCs typically appear as open sores (possible oozing or crusting) that don't heal or recur; raised red patches that may itch; pink, red, translucent, shiny or pearly bumps with possible darker areas; pink growths with raised edges; or scar-like lesions. They can be fragile and bleed easily such as with shaving or a minor injury. BCCs tend to develop on sun-exposed body areas, most commonly the face, head and neck. Slow-growing cancers, BCCs rarely metastasize to body regions beyond the original lesion site but have the potential to do so if left untreated. Delayed or ineffective treatment can also lead to disfigurement of the lesion. If not removed completely, BCCs can recur in the same location. Prior BCCs increase the likelihood of future BCCs.

### **1.3. SQUAMOUS CELL CARCINOMA (SCC)**

Squamous cell carcinomas (SCC) are uncontrolled growths of abnormal cells arising from the squamous cells in the epidermis producing keratin. SCCs may appear as scaly red patches (that may crust or bleed); open sores (possibly oozing or crusting) that don't heal or recur; or wart-like or elevated growths with a central depression. SCCs typically develop on sun-exposed body areas such as the face, ears, neck, lips, back of the hands, arms and legs. The skin in these areas often contain signs of sun damage such as wrinkles, pigment changes, freckles, "age spots," loss of elasticity and broken blood vessels. SCCs may also develop in scars or chronic skin sores elsewhere on the body, including the genitals, and occasionally in actinic keratoses. The natural history of SCCs also varies, from slowly enlarging to rapidly growing with significant tenderness and pain. They may become disfiguring and fatal if left untreated and allowed to grow.

#### **1.4. STATISTICS**

NMSC is the most commonly occurring type of skin cancer, and skin cancers are the most common of all types of cancer (about one-third of all cancers). It is estimated that about 3.3 million people in the United States (U.S.) are diagnosed with NMSC annually, equating about 5.4 million BCCs and SCCs. The diagnosis and treatment of NMSC in the U.S. increased by 77% between 1994 and 2014. It is believed that the increasing incidence of NMSC is due to better skin cancer detection, increasing sun exposure, and longer lifespans.

The incidence of basal cell carcinoma is about 4 times that of squamous cell carcinoma. An estimated 4.3 million cases of BCC are diagnosed annually in the U.S. resulting in over 3,000 deaths. Over 1 million cases of SCC are diagnosed in the U.S. annually, resulting in over 15,000 deaths. SCC has a 4% annual incidence of metastasis.

About 90% of NMSC is associated with exposure to ultraviolet (UV) radiation from the sun.

#### **1.5. CAUSE OF NON-MELANOMA SKIN CANCER (NMSC)**

NMSC primarily results from repeated and unprotected skin exposure to ultraviolet (UV) rays from sunlight and man-made sources such as tanning beds. UV rays can damage the DNA inside skin cells that comprise genes that control cell function.

It is believed that most NMSC are the result of DNA changes from UV ray exposure that affect the tumor suppressor genes in cells. Tumor suppressor genes are those that keep cell growth in check by slowing down cell division or causing cells to die at the right time. The gene most often altered in SCC is TP53, the tumor suppressor gene that normally functions to cause cells with damaged DNA to die. When TP53 is altered, these abnormal cells may live longer and proceed to become cancerous.

In BCC, the most common mutated gene is PTCH1, a tumor suppressor gene that typically functions to keep cell growth in check. Changes to PTCH1 permit cells to grow out of control.

These are not the only gene changes that play a role in the development of skin cancer. There are likely to be many others as well.

Additional risk factors for the development of NMSC include radiation therapy, lighter skin, prolonged immunosuppression, human immunodeficiency virus (HIV), human papilloma virus (HPV), and certain syndromes or genetic disorders.

Increased risk of multiple NMSC lesions is associated with males, tumor locations in the trunk and extremities, superficial histologic subtype, younger age at initial diagnosis, and red hair phenotype.

### **1.6. CONFIRMATORY DIAGNOSIS OF NMSC**

Dermoscopy is commonly used as an initial aid for early evaluation, identification and diagnosis of NMSC. Confirmatory diagnosis is subsequently made through clinical (physical) examination followed by histological excision (biopsy – most commonly punch or shave biopsy).

- (i) Clinical assessment of the lesion involves evaluation of tumor size (diameter) and anatomical location; determination of lesion recurrence; determination of lesion connection to underlying structures such as muscle, cartilage or bone; classification/grading of the borders (SCCs); and notation of evidence of prior surgery or treatment. If an SCC is suspected, lymph nodes are examined for potential metastasis.
- (ii) Histological examination of NMSC is critical to confirming the clinical assessment, confirming the histopathological type as BCC or SCC, and if applicable, the degree of differentiation of SCC. Histopathological assessment involves evaluation of tumor depth; presence of ulceration (BCCs); morphological subtype; histopathological features (SCCs); and perineural or vascular involvement.

### 1.7. BCC AND SCC VARIANTS

BCC and SCC variants are listed in the table below.

BCC Variants	SCC Variants
BCC nodular	SCC in situ/Bowen's disease
BCC superficial	SCC invasive
BCC infiltrative/Morpheaform	SCC clear-cell
BCC Basosquamous (metatypical) carcinoma	SCC Spindle Cell
BCC spindle cell	SCC De Novo
BCC carcinosarcoma	SCC lymphoepitheliomatous
BCC pigmented	SCC Verrucous
BCC micronodular	SCC Acantholytic
BCC trichoblastic	SCC Desmoplastic
BCC with follicular differentiation	SCC HPV induced
Fibroepithelioma of pinkus	SCC bowenoid papulosis
BCC cystic	
BCC adenoid cystic	
BCC keloidal	

### 1.8. TREATMENT OPTIONS

The range of available treatment options for NMSC includes surgery, cryotherapy, curettage and electrodesiccation, radiation therapy including superficial radiation therapy, photodynamic therapy, various forms of brachytherapy, and chemotherapeutic agents. Treatment decisions may be based on tumor type, anatomical location, patient age, tumor stage and classification, physician preference, and treatment setting. The choice of treatment becomes more complex among the elderly due to frailty, limited life-expectancy, and comorbidities. Anatomical location also becomes an important factor as NMSC lesions commonly occur on the ears, eyes and nose where treatment may have significant cosmetic consequences.

This study will focus on evaluation of outcomes of Superficial X-ray Therapy (SRT), a non-surgical option for patients with primary non-aggressive BCC and SCC and for patients who decline surgery or are poor surgical candidates.

## 2 STUDY JUSTIFICATION AND RATIONALE

Non-melanoma skin cancers are the most common form of cancers with the incidence increasing at a rapid rate. Current guidelines (e.g. National Comprehensive Cancer Network (NCCN) and American Academy of Dermatology (AAD)) suggest that surgical treatments remain the most effective option for the management of most cases of BCC and SCC.

Clinical recommendations for radiation therapy (RT) are typically based on consideration of RT as a single category without differentiating between the different applications of the different available modalities. As different radiotherapy modalities and dosing have been shown to result in widely varying outcomes, with recurrence rates ranging from 2.8% to 30%, such generalized recommendations can be misleading. AAD guidelines group newer technologies such as high-dose electronic brachytherapy (EBT) and SRT as new therapies. Though the AAD has since clarified these modalities in an addendum position statement it continues to refer to SRT as a “new” technology that “differs substantially from traditional external beam radiation therapy” and one in need of “research on long term outcomes.”

This retrospective study has been designed to focus on efficacy and safety of superficial radiation therapy (SRT) for NMSC and to specifically address this AAD-highlighted deficiency and need for long-term evaluation of ‘new’ technologies for the treatment of NMSC. Evaluation of SRT for NMSC in this study will be via review of retrospective data for procedures delivered by the Sensus Healthcare SRT-100™. Sensus Healthcare’s SRT-100™ has been cleared by the U.S. Food and Drug Administration (U.S. FDA) for the treatment of non-melanoma skin cancer and keloids.

The SRT-100™ delivers a precise, calibrated dose of superficial radiation therapy that only penetrates skin deep, resulting in a virtually painless treatment can be safely administered in the physician’s office.

Low-dose SRT effectively destroys BCC and SCC without any invasive cutting, bleeding or stitching. There is no need for anesthesia, no risk of infection or scarring and no need for reconstructive plastic surgery. Healing time is quick with minimal to no post-treatment downtime or lifestyle restrictions. It is therefore both a viable and highly desirable alternative to invasive, painful and higher-risk surgical procedures.

While formal long-term outcome evaluations may be lacking, there is much existing data. This study will utilize retrospective chart analysis to evaluate the outcomes of SRT-100™ therapy on NMSC lesions over a long-term post-treatment period. Long-term cure rate is considered the primary outcome, with secondary outcome evaluation focused on the impact on cure rate and other treatment outcomes of key variables such as lesion type, location, patient characteristics and treatment parameters such as treatment dosing and fractionation.

### 3. SUPPORTIVE LITERATURE

The following study published in 2012 is similar in design and purpose to the current retrospective trial.

Superficial x-ray in the treatment of basal and squamous cell carcinomas: A viable option in select patients

J Am Acad Dermatol December 2012 Volume 67, Issue 6, Pages 1235–1241

[name], Brett M. Howard, BA, Henry P. Heaton, BA, [name], Hyokyong [name], and W. [name]

The abstract from this publication is presented below.

*Background:* Effective nonsurgical modalities are limited in the treatment of basal cell carcinoma (BCC) and squamous cell carcinoma (SCC).

*Objective:* We sought to evaluate the efficacy and viability of superficial x-ray therapy in the treatment of BCC and SCC in an outpatient setting.

*Methods:* A retrospective analysis was performed on 1715 histologically confirmed primary cutaneous BCC and SCC treated with superficial x-ray therapy at Dermatology Associates of Tallahassee in Florida between 2000 and 2010.

*Results:* Of the 1715 tumors reviewed during this period, 712 were histologically proven BCC (631 nodular and 81 superficial), 994 were SCC (861 SCC in situ and 133 invasive SCC), and 9 displayed distinct features of both BCC and SCC in the same biopsy specimen. Kaplan-Meier estimates (with 95% confidence intervals) of cumulative recurrence rates of all tumors at 2 and 5 years were 1.9% (1%-2.7%) and 5.0% (3.2%-6.7%), respectively; of BCC at 2 and 5 years were 2% (0.8%-3.3%) and 4.2% (1.9%-6.4%),

respectively; and of all SCC at 2 and 5 years were 1.8% (0.8%-2.8%) and 5.8% (2.9%-8.7%), respectively. Tumors on male patients and those with a diameter greater than 2 cm were associated with a statistically significant increase in recurrence likelihood.

*Limitations:* This study represents only patients treated in 1 dermatology office in North Florida and may not be representative of the general patient population.

*Conclusions:* Superficial x-ray therapy remains a viable nonsurgical option for the treatment of primary BCC and SCC in patients where surgical intervention is declined, inadvisable, or potentially associated with significant cosmetic or functional limitations.

The present study's design and intent is to confirm and expand upon these findings. In particular, the limitation of the prior study of homogeneity of the population source from which the data was drawn will be overcome in the present study, as data from numerous sources will be collated and evaluated collectively such that the findings will be representative and generalizable to the general patient population.

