### **5.2. INVESTIGATIONAL PLAN**

#### **5.2.1. Collecting Sites**

There will be multiple participating sites located in the United States selected based upon having access to the required patient population medical records. There is no limit on the potential number of participating sites. Each identified and qualifying site that is willing to participate in the study will be included.

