### **5.3.2. Total Number of Study Sites/Total Number of Subjects Projected**

There will be multiple participating study sites, all located in the United States. Each will be selected based upon having access to the required medical records of patients who were treated at their site for NMSC with the SRT-100™ prior to January 1, 2015, and for whom follow-up data is available. There is no limit on the potential number of participating sites. Each identified and qualifying site that is willing and able to participate in the study will be included.

Subject data will be retrospectively collected from the existing medical records in the identified qualifying patient files at the participating sites as those who were treated with the SRT-100™ for one or more NMSCs, who have follow-up data and who subsequently satisfy all of the inclusion criteria and none of the exclusion criteria for inclusion of their retrospective data in this study. There is no limit on the potential number of study subjects. The applicable retrospective data for each identified and qualifying subject at each participating study site will be included in the retrospective analysis.

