#### **10.1.2. Recurrences and Complications**

Each identified incidence of lesion recurrence, complication or adverse event recorded at any point throughout the treatment and follow-up evaluation phase will be explored descriptively. Statistical evaluation of recurrences will be as follows:

- (i) *Kaplan-Meier Survival Probability Estimates* will be calculated across the duration of available follow-up data, reporting survival probability estimates, and lower and upper limits of the 95% Confidence Interval by follow-up year.
- (ii) *Log-Rank Test* will be performed to evaluate for differences in recurrence-free survival between lesion types.
- (iii) *Multivariate Cox Regression Analysis* will be performed to account for the contribution of the potential influential factors of gender, age, lesion type, lesion size, total treatment dosage and TDF to recurrence-free survival.

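### Pooling volunteer sites does not make the findings representative, and no planned analysis uses site, so dominance by one site or differences between sites would go unseen.

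*Combined protocol and SAP*

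**What the plan says.** Section 3 summarises a retrospective study of 1715 tumours and quotes its stated limitation: "This study represents only patients treated in 1 dermatology office in North Florida". The text that follows presents the use of numerous sources as the particular advance of the present study, "such that the findings will be representative and generalizable to the general patient population".

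Site entry is described twice. Section 5.2.1 says sites are "selected based upon having access to the required patient population medical records" and that "Each identified and qualifying site that is willing to participate in the study will be included". Section 5.3.2 repeats this with one added condition: "Each identified and qualifying site that is willing and able to participate in the study will be included". Neither sites nor subjects have a target: "There is no limit on the potential number of participating sites" and "There is no limit on the potential number of study subjects".

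Charts are filtered further. Sections 5.3.2 and 5.4 require follow-up data, and inclusion criterion 7 in section 5.4.1 requires the necessary data to be present and sufficient. Within a site, every qualifying chart is taken.

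In section 10.1, cure rate is a single percentage over all lesions, the Kaplan-Meier estimates with 95% limits are pooled, and the log-rank test compares lesion types. The Cox model covers "the potential influential factors of gender, age, lesion type, lesion size, total treatment dosage and TDF to recurrence-free survival". Section 10.2 is descriptive, with t-tests between lesion types. Location in section 10.2.2 means body location.

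**The concern.** The statement in section 3 is a claim about inference: results from this set of charts are said to carry over to patients in general. That needs either a sampling scheme or some evidence on who was left out, and the plan has neither.

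The claim also rests on having many sources, yet nothing in the planned output would show how many sites contributed, how lesions were spread over them, or whether outcomes differed. If one practice supplied most lesions, the limitation of the earlier study would return without being visible in the report.

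At stake are the scope of the conclusion, the honesty of the intervals if they are read as applying to SRT-100 practice at large, and the interpretation of the dosage and TDF effects, which bear on a secondary objective.

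**Working it through.** The plan states no sample size, number of sites, event count or precision target, so there is no figure to reproduce. The check is a reading of the text followed by an illustration on assumed inputs.

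**1. Does the design support representativeness?**
- Sampling frame for sites: none. Entry is by access to records and willingness (5.2.1, 5.3.2).
- Spread by region or practice type: none required beyond location in the United States.
- Charts: limited to those with follow-up and sufficient data (5.4, 5.4.1). No comparison of included with excluded charts is planned.
- Weighting, or comparison with an external population: none in section 10.

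**2. Does any analysis use site?** No analysis from 10.1.1 to 10.2.4 has a site term, stratum, table or cluster adjustment. Site is not a data element in section 6.3. It survives only through the investigator's initials in the patient code (7.2.1), and the sheets linking codes to charts are destroyed after data checking.

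**3. What could ignoring site do to a pooled rate?** Inputs:
- Recurrence p = 0.05, from the 5-year estimate of 5.0% in the earlier study (section 3).
- Lesions per site m = 50 or 170: assumed.
- Intraclass correlation (ICC) 0.005 or 0.02: assumed.
- Equal site sizes and no censoring: assumed.

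Design effect = 1 + (m − 1) × ICC; the standard error ratio is its square root; between-site SD = √(ICC × p × (1 − p)).

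| m | ICC | Between-site SD | Design effect | SE ratio |
|---|---|---|---|---|
| 50 | 0.005 | 1.5 points | 1 + 49 × 0.005 = 1.25 | 1.1 |
| 50 | 0.02 | 3.1 points | 1 + 49 × 0.02 = 1.98 | 1.4 |
| 170 | 0.005 | 1.5 points | 1 + 169 × 0.005 = 1.85 | 1.4 |
| 170 | 0.02 | 3.1 points | 1 + 169 × 0.02 = 4.38 | 2.1 |

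These ratios apply to a pooled proportion, and only when the target extends to sites outside the study.

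**4. Does the same hold for the Cox model?** Not in general. In a simulation with 10 sites of 170 lesions, about 4.5% events and a between-site coefficient of variation of 0.31 or 0.62 (1.5/5 and 3.1/5, up to rounding), the ratio of true to reported standard error was 1.00 and 0.99 for a covariate balanced within sites. For a covariate constant within each site it was 1.22 and 1.88. The exact values depend on the assumed set-up; the contrast is what matters. Total dosage and TDF may be close to the second case if they follow a site's practice. They may also be confounded with other features of the site.

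**5. Can site analysis repair selection?** No. Suppose participating sites have 5.0% recurrence, half the target population is treated elsewhere, and the rate there is 1.5 to 3 times as high (all assumed). The overall rate would be 0.5 × 5.0 + 0.5 × 7.5 = 6.3%, up to 0.5 × 5.0 + 0.5 × 15.0 = 10.0%. Neither more lesions nor a site term would reveal this.

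**The case against.** The strongest reply is that the sentence is background text, not an objective, and that section 10 draws no conclusion about generalisability. Several sites do reduce reliance on one office. Within a site all qualifying charts are taken, so patients do not select themselves. This stands in part: the single-office limitation is lessened. But the text says it is overcome and presents this as the study's particular advance.

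A second reply is that stratified models and leave-one-site-out checks compare participating sites only and do not test representativeness. That is correct. Narrowing the claim and reporting selection address external validity; the site analyses address heterogeneity and dominance.

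A third is that once the target is restricted to the participating sites, variation between them is not sampling error and the inflation in the table does not apply. That is also correct, and the table should be read only for wider inference.

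A reader might infer more than the documents support:
- That all Cox and log-rank results are too precise. Little inflation is expected for factors that vary within site, as gender, age, lesion type and lesion size ordinarily would.
- That the recurrence range of 2.8% to 30% in section 2 shows how much sites differ. It spans different radiotherapy modalities and dosing, whereas this study has one modality and one device.
- That sites own the sponsor's device. The protocol says only that they treated patients with it.

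**Conclusion.** The concern holds in a limited form. The representativeness asserted in section 3 is not a property of this design: sites are a non-probability set of willing SRT-100 users, charts are filtered on follow-up and completeness, and the analysis would not show whether one site dominates.

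For inference beyond the participating sites, the pooled Kaplan-Meier intervals, and any interval placed on the cure rate, are too narrow if outcomes differ between sites. The illustrated factor of about 1.1 to 2.1 rests wholly on assumed site sizes and ICC; the documents give neither. In the Cox model the exposure is confined mainly to total dosage and TDF, through confounding with site or understated standard errors. The study can proceed, but the plan should be changed, because this alters what it can conclude.

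**What to change.** 1. **Section 3:** restate the claim as applying to patients with recorded follow-up at participating SRT-100 sites, with the single-office limitation lessened and not overcome.
2. **Sections 6.3 and 7.2.1:** add an unambiguous site code to the database before the link sheets are destroyed. Initials may be enough, but two investigators could share them, and a separate code removes the doubt.
3. **Section 10.1:** report lesions, recurrences and cure rate by site. Where records allow, also report sites approached against sites participating, and charts screened against charts included.
4. **Section 10.1.2:** as sensitivity analyses, add a site-stratified log-rank test and Cox model, and a leave-one-site-out check of the primary estimates. If the number of sites allows, add a site-cluster-robust or bootstrap interval for the pooled rates. Read the dosage and TDF terms alongside the stratified model.

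The cost is one column and a modest amount of analysis; the site analyses need no further chart review. Intervals may widen. At 5% recurrence, 50 to 170 lesions give only about 2.5 to 8.5 recurrences per site (50 × 0.05 and 170 × 0.05), so site-specific estimates will be imprecise and should be presented descriptively. Dosage or TDF effects may be poorly estimated after stratification if they hardly vary within site, which would itself be worth reporting. The generalisability claim becomes narrower.
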